- 110 Adequate organ function determined \leq 3 weeks prior to enrollment defined as follows:

Hematological:

- Absolute neutrophil count (ANC) \geq $1.0 \times 10^9/L$
- Platelet count \geq $75 \times 10^9/L$
- Hemoglobin \geq 8 g/dL

Renal:

- Creatinine clearance \geq 50 mL/min Cockcroft-Gault equation

Hepatic:

- Aspartate aminotransferase (AST) and alanine aminotransferase (ALT) < 3 x upper limit of normal (ULN)
- Total bilirubin < 2 x ULN (unless Gilbert's Disease or if liver involvement with lymphoma)

111 Subject will be available to complete all protocol-required study visits or procedures, and/or to comply with all required study procedures to the best of the subject's and investigator's knowledge including but not limited to:

- Completion of up to a 24-month run-in period
- Completion of all regularly scheduled study visits including blood draws for MRD assessment, clinical disease state assessment, PET-CT scans (ie, at time of MRD positivity or relapse), assignment to treatment with blinatumomab

4.1.2 Exclusion Criteria – Part 1

- 201 Clinically relevant CNS pathology such as epilepsy, seizure, paresis, aphasia, stroke, severe brain injury, dementia, Parkinson's disease, cerebellar disease, organic brain syndrome, and psychosis
- 202 Evidence of CNS involvement with DLBCL **at disease evaluation obtained prior to starting blinatumomab**
- 203 Current autoimmune disease or history of autoimmune disease with potential of CNS involvement
- 204 Prior anti-CD19 directed therapies
- 205 Prior alloHSCT
- 206 Received radiation \leq 2 weeks prior to enrollment
- 207 Infection with human immunodeficiency virus or chronic infection with hepatitis B virus (hepatitis B surface antigen positive) or hepatitis C virus (anti-hepatitis C virus positive)
- 208 History of malignancy other than DLBCL within the past 3 years with the following exceptions:
- Malignancy treated with curative intent and with no known active disease present for \geq 3 years before enrollment and felt to be at low risk for recurrence by the treating physician
 - Adequately treated non-melanoma skin cancer or lentigo maligna without evidence of disease
 - Adequately treated cervical carcinoma in situ without evidence of disease

- Adequately treated breast ductal carcinoma in situ without evidence of disease
 - Prostatic intraepithelial neoplasia without evidence of prostate cancer
 - Adequately treated urothelial papillary noninvasive carcinoma or carcinoma in situ

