	Seizure ^a	
 Interrupt blinatumomab, administer corticosteroids (refer to Table 2) and anti-seizure medication per local practice For restart, refer to grade 3 neurologic events above for dose level rules for re-instituting infusion Do not re-initiate blinatumomab until 7 days after the last seizure and after therapeutic levels of anti-seizure medication are likely to have been achieved Permanently discontinue if a second seizure occurs with re-initiation of blinatumomab at any dose

Footnotes defined on last page

Table 1. Infusion Interruptions/Dose Modifications Due to Adverse Events

Toxicity	Grade or Adverse Event	Instructions for Treatment Interruption and Restart
Elevated liver enzymes	NA	
 • Interrupt blinatumomab (refer to Table 3) if any one of the following occurs: 
 ○ TBL > 3 x ULN at any time ○ ALP > 8 x ULN at any time ○ AST or ALT > 8x ULN at any time ○ AST or ALT > 5x ULN but < 8 x ULN for ≥ 2 weeks ○ AST or ALT > 3 x ULN with clinical signs or symptoms that are consistent with hepatitis (eg, RUQ abdominal pain/tenderness, fever, nausea, vomiting, jaundice) • Permanently discontinue blinatumomab if: 
 ○ TBL > 2 x ULN OR INR > 1.5 (for subjects not on anticoagulant therapy) AND ○ AST or ALT > 3 x ULN (when baseline was < ULN) AND ○ no other cause for the combination of the above laboratory abnormalities is immediately apparent 
Refer to Section 6.4 for additional details

Other clinically relevant adverse events	3	
 • Interrupt blinatumomab until event improves to grade ≤ 1 (refer to Table 2) • Restart no less than 72 hours after the initial observation of the grade 3 event at the following dose levels: 
 ○ If event occurred at 112 µg/day, resume at 28 µg/day ○ If event occurred at 9 or 28 µg/day, resume at 9 µg/day • Escalate up 1 dose level after 7 days if toxicity does not reoccur. Increase dose stepwise at 7-day intervals to target dose of 112 µg/day if toxicity does not reoccur. • Permanently discontinue blinatumomab if: 
 ○ Initial grade 3 event does not improve to grade ≤ 1 within 14 days, OR ○ Grade 3 event reoccurs at the lower dose level within 7 days of re-initiation OR ○ Grade 3 event reoccurs at a dose of 9 µg/day without prior -dose-step escalation

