6.2.1.3 Permanent Discontinuation of Blinatumomab

Blinatumomab will be permanently discontinued for:

Disease Progression

Cytokine Release Syndrome

- Initial grade 3 CRS that does not improve to grade ≤ 1 within 7 days
- Grade 3 CRS that reoccurs at the lower dose level within 7 days of reinitiation
- Grade 3 CRS reoccurs at a dose of 9 $\mu\text{g}/\text{day}$ without prior dose-step escalation
- Grade 4 CRS

Neurologic Events

- Initial grade 3 neurologic event occurred at 9 $\mu\text{g}/\text{day}$
- Initial grade 3 neurologic event does not improve to grade ≤ 1 within 7 days
- Grade 3 neurologic event that reoccurs at the lower dose level within 7 days of reinitiation
- Grade 3 neurologic event reoccurs at a dose of 9 $\mu\text{g}/\text{day}$
- Grade 4 neurologic event
- A second seizure occurs after reinitiation of blinatumomab at any dose

Elevated Liver Enzymes

- Total bilirubin (TBL) $> 2 \times$ ULN OR international normalized ratio (INR) > 1.5 (for subjects not on anticoagulant therapy) AND
- AST/ALT $> 3 \times$ ULN (when baseline was $< \text{ULN}$) AND
- No other cause of combination of the above laboratory abnormalities is immediately apparent

Other Clinical Relevant Adverse Events

- Initial grade 3 event does not improve to grade ≤ 1 within 14 days (with the exception of delay in restart due to logistical difficulties, in which case the restart may be postponed for an additional 7 days)
- Grade 3 event reoccurs at the lower dose level within 7 days of reinitiation
- Grade 3 event reoccurs at a dose of 9 $\mu\text{g}/\text{day}$ without prior dose-step escalation
- Dose limiting toxicities (DLTs) as described in [Section 6.2.2](#)

Subjects who permanently discontinue study treatment due to adverse event should continue with other study procedures, including response assessment, as appropriate.

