6.2.2 Study Stopping Rules

The DLT evaluation period will be the entire duration of cycle 1 of blinatumomab treatment. For subjects who are removed from study treatment for reasons other than an adverse event/toxicity, ie, disease progression, they will be considered DLT evaluable if they have received at least 7 days of the target dose of blinatumomab.

The occurrence of any of the following toxicities will be considered a DLT, if judged by the investigator to be related to blinatumomab administration:

- grade 5 toxicity
- grade 4 non-hematologic toxicity (non-laboratory)
- grade 4 hematologic toxicity lasting ≥ 7 days (**excluding lymphopenia**)
- grade 4 laboratory abnormalities lasting ≥ 7 days (**excluding lymphopenia**)
- any permanent discontinuation of blinatumomab as described in [Section 6.2.1.3](#)

The stopping rules will use a Bayesian approach to terminate the study if the posterior probability that the DLT rate is greater than 25% is $> 90\%$ ([Section 10.3.1](#)).

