6.4 Hepatotoxicity Stopping and Rechallenge Rules

Subjects with abnormal hepatic laboratory values (ie, alkaline phosphatase [ALP], AST, ALT, TBL) and/or international normalized ratio [INR] and/or signs/symptoms of hepatitis (as described below) may meet the criteria for withholding or permanent discontinuation of Amgen investigational product or other protocol-required therapies as specified in the Guidance for Industry Drug-Induced Liver Injury (DILI): Premarketing Clinical Evaluation, July 2009.

6.4.1 Criteria for Withholding and/or Permanent Discontinuation of Amgen Investigational Product and Other Protocol-required Therapies Due to Potential Hepatotoxicity

The following stopping and/or withholding rules apply to subjects for whom another cause of their changes in liver biomarkers (TBL, INR and transaminases) has not been identified.

Important alternative causes for elevated AST/ALT and/or TBL values include, but are not limited to:

- Hepatobiliary tract disease
- Viral hepatitis (eg, Hepatitis A/B/C/D/E, Epstein-Barr Virus, cytomegalovirus, Herpes Simplex Virus, Varicella, toxoplasmosis, and Parvovirus)

- Right sided heart failure, hypotension or any cause of hypoxia to the liver causing ischemia.
- Exposure to hepatotoxic agents/drugs or hepatotoxins, including herbal and dietary supplements, plants and mushrooms
- Heritable disorders causing impaired glucuronidation (eg, Gilbert's Syndrome, Crigler-Najjar syndrome) and drugs that inhibit bilirubin glucuronidation (eg, indinavir, atazanavir)
- Alpha-one antitrypsin deficiency
- Alcoholic hepatitis
- Autoimmune hepatitis
- Wilson's disease and hemochromatosis
- Nonalcoholic Fatty Liver Disease including Steatohepatitis (NASH)
- Non-hepatic causes (eg, rhabdomyolysis, hemolysis)

If investigational product(s) is/are withheld, the subject is to be followed according to recommendations in [Appendix A](#) for possible DILI.

Rechallenge may be considered if an alternative cause for impaired liver tests (ALT, AST, ALP) and/or elevated TBL, is discovered and the laboratory abnormalities resolve to normal or baseline ([Section 6.4.2](#)).

Table 3. Conditions for Withholding and/or Permanent Discontinuation of Amgen Investigational Product and Other Protocol-required Therapies Due to Potential Hepatotoxicity

Analyte	Temporary Withholding	Permanent Discontinuation
TBL	> 3 x ULN at any time	> 2 x ULN
		OR
INR	--	> 1.5 (for subjects not on anticoagulation therapy)
	OR	AND

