AST/ALT	> 8 x ULN at any time > 5 x ULN but < 8 x ULN for ≥ 2 weeks > 5 x ULN but < 8 x ULN and unable to adhere to enhanced monitoring schedule > 3 x ULN with clinical signs or symptoms that are consistent with hepatitis (such as right upper quadrant pain/tenderness, fever, nausea, vomiting, jaundice).	In the presence of no important alternative causes for elevated AST/ALT and/or TBL values > 3 x ULN (when baseline was < ULN)
	OR	
ALP	> 8 x ULN at any time	--

ALP = alkaline phosphatase; ALT = alanine aminotransferase; AST = aspartate aminotransferase; INR = international normalized ratio; TBL = total bilirubin; ULN = upper limit of normal

6.4.2 Criteria for Rechallenge of Amgen Investigational Product and Other Protocol-required Therapies After Potential Hepatotoxicity

If signs or symptoms recur with rechallenge, then blinatumomab and other protocol-required therapies, as appropriate should be permanently discontinued.

Subjects who clearly meet the criteria for permanent discontinuation (as described in [Table 3](#)) should never be rechallenged.

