9.2.2 Adverse Events

9.2.2.1 Reporting Procedures for Adverse Events That do not Meet Serious Criteria

The investigator is responsible for ensuring that all adverse events observed by the investigator or reported by the subject that occur after first dose of blinatumomab through the safety follow-up visit are reported using the Event CRF.

The investigator must assign the following adverse event attributes:

- adverse event diagnosis or syndrome(s), if known (if not known, signs or symptoms)
- dates of onset and resolution (if resolved)
- severity (and/or toxicity per protocol)
- assessment of relatedness to investigational product(s), medical device(s) or other protocol-required therapies
- action taken.

The adverse event grading scale used will be the Common Terminology Criteria for Adverse Events (CTCAE) version 4.0. The grading scale used in this study is described in [Appendix A](#).

The investigator must assess whether the adverse event is possibly related to the investigational product(s), and/or other protocol-required therapies. This relationship is indicated by a “yes” or “no” response to the question: Is there a reasonable possibility that the event may have been caused by the investigational product(s), and/or other protocol-required therapies?

The investigator is responsible for reviewing laboratory test results and determining whether an abnormal value in an individual study subject represents a clinically significant change from the subject's baseline values. All grade 3 and grade 4 laboratory values should be recorded as adverse events. In addition, if signs or symptoms are associated with the laboratory abnormality, the signs/symptoms and the laboratory abnormality should all be recorded as adverse events. The laboratory abnormality and any signs/symptoms should be graded according to their own CTCAE criteria.

The investigator is expected to follow reported adverse events until stabilization or reversibility.

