14. APPENDICES

Appendix A. Additional Safety Assessment Information

Adverse Event Grading Scale

Refer to the National Cancer Institute Common Terminology Criteria for Adverse Events (CTCAE) version 4.0 for adverse event grading and information. The CTCAE scale is available at the following location:

http://ctep.cancer.gov/protocolDevelopment/electronic_applications/ctc.htm

Drug-induced Liver Injury Reporting & Additional Assessments

Reporting

To facilitate appropriate monitoring for signals of Drug Induced Liver Injury (DILI), cases of concurrent AST or ALT and total bilirubin and/or international normalized ratio (INR) elevation according to the criteria specified in [Section 6.4](#) require the following:

- The event is to be reported to Amgen as a serious adverse event within 24 hours of discovery or notification of the event (ie, before additional etiologic investigations have been concluded)
- The appropriate case report form (CRF) (eg, Event CRF) that captures information necessary to facilitate the evaluation of treatment-emergent liver abnormalities is to be completed and sent to Amgen.

Other events of hepatotoxicity and potential DILI are to be reported as serious adverse events if they meet the criteria for a serious adverse event defined in [Section 9.1.3](#).

Additional Clinical Assessments and Observation

All subjects in whom investigational product(s) or protocol-required therapies is/are withheld (either permanently or conditionally) due to potential DILI as specified in [Table 3](#), or who experience AST or ALT elevations > 3 x ULN or 2-fold increases above baseline values for subjects with elevated values before drug are to undergo a period of “close observation” until abnormalities return to normal or to the subject’s baseline levels.

Assessments that are to be performed during this period include:

- Repeat AST, ALT, ALP, bilirubin (total and direct), and INR within 24 hours
- In cases of TBL > 2 x ULN or INR > 1.5, retesting of liver tests, bilirubin (total and direct), and INR is to be performed every 24 hours until laboratory abnormalities improve

Testing frequency of the above laboratory tests may decrease if the abnormalities stabilize or the investigational product(s) or protocol-required therapies has/have been discontinued AND the subject is asymptomatic.

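### The combined liver stop rule leaves a narrow range with no mandated action for eligible subjects whose baseline AST/ALT is at or above ULN

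*Protocol*

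**What the plan says.** The combined permanent stop has three conditions: bilirubin > 2 x ULN or INR > 1.5 (subjects not on anticoagulants); AST/ALT > 3 x ULN; and no other explanation. It appears in three places, each time with a baseline limit on the transaminase condition.

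- Table 1 (Section 6.2.1.2.2): "AST or ALT > 3 x ULN (when baseline was < ULN").
- Section 6.2.1.3: the same limit, followed by the third condition, "No other cause of combination of the above laboratory abnormalities is immediately apparent".
- Table 3 (Section 6.4.1), where the cause condition and the threshold share one cell: "In the presence of no important alternative causes for elevated AST/ALT and/or TBL values > 3 x ULN (when baseline was < ULN").

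Criterion 110 admits "Aspartate aminotransferase (AST) and alanine aminotransferase (ALT) < 3 x upper limit of normal (ULN"), and criterion 114 repeats that ceiling before treatment assignment. Both also require total bilirubin < 2 x ULN, except with Gilbert's disease or liver involvement.

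The interruption rules in Tables 1 and 3 carry no baseline limit. They apply at bilirubin > 3 x ULN, at ALP > 8 x ULN, at AST/ALT > 8 x ULN, at AST/ALT between 5 and 8 x ULN for 2 weeks or more (Table 3 adds: or if enhanced monitoring cannot be followed), and at AST/ALT > 3 x ULN with clinical hepatitis. Table 3 gives no withholding threshold for INR.

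Appendix A does recognise raised baselines. Its trigger for close observation includes "2-fold increases above baseline values for subjects with elevated values before drug".

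**The concern.** Two subjects with identical on-treatment liver results can be handled in opposite ways because of their baseline. The normal-baseline subject is stopped, may never be rechallenged, and counts as a DLT if the event is judged related, because Section 6.2.2 lists "any permanent discontinuation of blinatumomab as described in" Section 6.2.1.3. The raised-baseline subject may stay on the infusion under the written rules, and no DLT arises by this route.

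The entry limits make the contrast sharper. Leaving aside Gilbert's disease and liver involvement, a subject with AST/ALT > 3 and bilirubin > 2 x ULN has crossed both ceilings for starting treatment, yet no rule requires treatment to pause.

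Reporting may be affected too. Appendix A ties its 24-hour report of possible drug-induced liver injury to the Section 6.4 criteria, so these subjects may fall outside it.

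**Working it through.** This is a check of decision rules; the plan gives no figure to reproduce. All values are multiples of ULN, except INR.

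**Inputs.** Stop and interruption thresholds come from Protocol Tables 1 and 3 and Section 6.2.1.3, and entry ceilings from criteria 110 and 114. Grades come from SAP Table 14-1: AST/ALT > 3 to 5 is grade 2, and bilirubin > 1.5 to 3 is grade 2.

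**Step 1: same results, different baseline.** The subject has no hepatitis signs, ALP at most 8 and no other cause. AST/ALT is 4.5 and bilirubin 2.5.

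| Baseline AST/ALT | Fold rise | Mandated action |
|---|---|---|
| 0.9 | 4.5/0.9 = 5.0 | permanent stop |
| 1.0 | 4.5/1.0 = 4.5 | none |
| 1.5 | 4.5/1.5 = 3.0 | none |
| 2.0 | 4.5/2.0 = 2.25 | none |
| 2.5 | 4.5/2.5 = 1.8 | none |

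The interruption rules are silent because 2.5 is not above 3 for bilirubin and 4.5 is not above 5 for AST/ALT. Both values are grade 2, so the general grade 3 row of Table 1 is not reached on laboratory values.

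**Step 2: the INR condition.** With AST/ALT 4, INR 1.6 and bilirubin 1, baseline 0.8 gives a permanent stop. Baselines 1.0, 1.5 and 2.9 give no liver-rule action. The documents give no INR grades, so this part of the gap holds only while INR is below grade 3. It also needs bilirubin at or below 3.

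**Step 3: the edges of the gap, baseline 1.5.**

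- AST/ALT 4.5 with bilirubin 3.2: interruption on bilirubin alone.
- AST/ALT 4 and bilirubin 2.5 with hepatitis signs: interruption.
- AST/ALT 8.1: interruption on AST/ALT alone.
- AST/ALT 5.1: interruption only if handled under the general grade 3 row. Section 9.2.2.1 supports that reading: "All grade 3 and grade 4 laboratory values should be recorded as adverse events". If that row is read as not covering liver enzymes, the gap extends to just under 8 for less than 2 weeks. The upper limit of 5 used here is the cautious one.

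**Step 4: what a 2-fold clause would cover.** The clause acts from max(3, 2 x baseline). Share of the > 3 to 5 band covered = (5 − start)/(5 − 3).

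| Baseline | Start | Share of band |
|---|---|---|
| 1.0 to 1.5 | 3.0 | 2.0/2 = 100% |
| 1.75 | 3.5 | 1.5/2 = 75% |
| 2.0 | 4.0 | 1.0/2 = 50% |
| 2.25 | 4.5 | 0.5/2 = 25% |
| 2.5 and above | 5.0 or more | 0% |

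These are widths of the band, not probabilities.

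**Step 5: how many subjects lack the rule.** The documents give no share with raised baseline. Assuming 5%, 10% or 20%: 30 x 0.05 = 1.5, 30 x 0.10 = 3, and 30 x 0.20 = 6 of 30 treated subjects. This counts subjects outside the combined stop, not subjects who reach the gap, who would be far fewer.

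**The case against.** The strongest reply is that the limit may be deliberate. It is written the same way three times, and Appendix A separately considers subjects with raised values before drug and assigns them close observation: repeat tests within 24 hours, then every 24 hours while bilirubin is > 2 x ULN or INR > 1.5. Section 6.4 also rests on an outside liver-injury guidance that cannot be consulted here. This stands as far as intent goes. A reader might infer an oversight, or infer that the 2-fold measure shows what the limit was meant to do. The documents support neither, since a 2-fold trigger for observation fits equally well with a choice of monitoring over stopping.

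A second reply is that the gap is narrow, and it is. A single hepatitis sign with AST/ALT > 3 x ULN, jaundice included, forces interruption at any baseline. Restart after withholding is limited: "Rechallenge may be considered if an alternative cause for impaired liver tests (ALT, AST, ALP) and/or elevated TBL, is discovered", and values must also return to normal or baseline. Some raised-baseline subjects will have a listed alternative cause, and then neither the present rule nor an extended one applies. Liver injury is a named example of a medically important serious event (Section 9.1.3), the Data Review Team sees all adverse events, and the investigator may remove a subject. These safeguards lower the risk, but none mandates interruption or a stop.

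Third, SAP Table 14-1 is an analysis table, while sites grade by CTCAE 4.0 and may record a diagnosis. A liver-injury diagnosis might be graded above its laboratory values and so reach the grade 3 row. That is possible but depends on site judgment; the laboratory values alone do not trigger it.

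**Conclusion.** The gap holds in bounded form. For baseline AST/ALT from ULN to < 3 x ULN, the rules mandate neither interruption nor stop when all of the following are true:

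- on-treatment AST/ALT is > 3 to 5 x ULN;
- bilirubin is > 2 to 3 x ULN, or INR is > 1.5 and below any grade 3 value with bilirubin at most 3 x ULN;
- ALP is at most 8 x ULN;
- there are no hepatitis signs and no alternative cause.

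It would be wrong to read this as raised-baseline subjects having no liver protection, since the interruption rules outside the range apply to them in full. Nor do the documents support a claim that many subjects are affected or that the DLT boundaries are materially distorted: the 5% to 20% shares are assumptions and no event rate is given. The primary MRD estimate is not at issue. What remains is an unlikely event with potentially serious harm and a cheap remedy, which makes this a worthwhile improvement rather than a critical defect.

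**What to change.** In Table 1, Section 6.2.1.3 and Table 3, add a clause for baseline AST/ALT at or above ULN. When AST/ALT is > 3 x ULN and at least 2 x baseline, with bilirubin > 2 x ULN or INR > 1.5 and no other cause, interrupt at once as a minimum, and discontinue permanently if no alternative cause is found. State that the same 24-hour liver-injury report applies. The DLT definition then follows through its reference to Section 6.2.1.3.

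The multiple is the one already in Appendix A; the exact value is a clinical choice. Rises under 2-fold, such as 2.5 to 4.5 x ULN, would stay under close observation. The band therefore remains partly uncovered for baselines between 1.5 and 2.5 x ULN, and essentially uncovered from about 2.5 x ULN upwards. If the sponsor prefers observation alone for raised baselines, the protocol should say so.

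The cost is one clause in three places at the next amendment. No new tests are needed, because chemistry is scheduled and Appendix A already requires INR during close observation. The downside is a few more interruptions, discontinuations and possible DLTs.
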